#### 9.2.11 Duration of hospital stay - days

Duration of hospitalization will be calculated only for participants who are discharged alive on or prior to Day 29 and will be compared between the treatment arms using negative binomial regression.

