3.7. Table of endpoints/outcomes

Objectives	Outcome Measures	Timepoint(s)
Primary Objective Participant clinical status (on a 7- point ordinal scale) In accordance with WHO recommendations the primary endpoint will be determined by a pilot trial of the first 100 participants.	 7-point ordinal scale: Not hospitalised, no limitations on activities Not hospitalised, limitation on activities; Hospitalised, not requiring supplemental oxygen; Hospitalised, requiring supplemental oxygen; Hospitalised, on non-invasive ventilation or high flow oxygen devices; Hospitalised, on invasive mechanical ventilation or ECMO (Extracorporeal membrane oxygenation) Death. 	Up to day 29
Secondary Objectives	Outcome Measures	Timepoint(s)
Evaluate the clinical efficacy of Brensocatib relative to standard care in adult patients hospitalised with COVID-19	Clinical Severity Time to an improvement of one category from admission using 7-point ordinal scale. Participant clinical status on 7-point ordinal scale Mean change in the 7-point ordinal scale	Daily whilst hospitalised Days 3, 5, 8, 11, 15 and 29. Baseline to days 3, 5, 8, 11, 15 and 29.
	National Early Warning Score (NEWS): Time to discharge or to a NEWS of ≤ 2 and maintained for 24 hours, whichever occurs first. Change from baseline Oxygenation:	Daily whilst hospitalised Days 8, 15, 29
	Oxygen free days Incidence and duration of new oxygen use during the trial	1-29 days 0-29 days
	Mechanical Ventilation: Ventilator free days	1-29 days

	Incidence and duration of new mechanical ventilation use during the trial.	1-29 days
	Hospitalisation:	
	Duration of hospitalisation (days).	Date of admission and discharge
	Mortality:	
	28-day mortality	Date of death
Evaluate the safety of the	Cumulative incidence of SAEs	1-29 days
intervention through 28 days of follow-up as compared to the control arm	Discontinuation or temporary suspension of treatment	1-29 days
	Changes in white cell count, haemoglobin, platelets, creatinine, total bilirubin, ALT, and AST over time (hospitalised participants only)	Days 0/1, 3, 5, 8, 11, 15, 29
	Adverse events of special interest- hyperkeratosis, infections and dental complications	1-29 days
	dental complications	
Exploratory Objectives	Outcome Measures	Timepoint(s)
Exploratory Objectives Evaluate the virologic efficacy of Brensocatib	·	Timepoint(s) Day 15 and day 29

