6.1. Inclusion criteria

- Male or female
- ≥16 years of age
- SARS-CoV-2 infection (clinically suspected* or laboratory confirmed*).
- Admitted to hospital as in-patient less than 96 hours prior to randomisation^
- Illness of any duration, and at least one of the following:
 - Radiographic infiltrates by imaging (e.g. chest x-ray, computed tomography (CT) scan)
 OR
 - Evidence of rales/crackles on physical examination
 - Peripheral capillary oxygen saturation (SpO2)≤94% on room air prior to randomization
 OR
 - Requiring supplemental oxygen.
 - Lymphocyte count <1 x 10⁹ cells per litre (L)
- Participant (or legally authorized representative) provides written informed consent
- Able to take oral medication
- Participant (or legally authorised representative) understands and agrees to comply with planned trial procedures.

*Laboratory-confirmed: SARS-CoV-2 infection as determined by polymerase chain reaction (PCR), or other commercial or public health assay in any specimen < 96 hours prior to randomization.

*Clinically suspected: in general, SARS-CoV-2 infection should be suspected when a patient presents with (i) typical symptoms (e.g. influenza-like illness with fever and muscle pain, or respiratory illness with cough and shortness of breath); and (ii) compatible chest X-ray findings (consolidation or ground-glass shadowing); and (iii) alternative causes have been considered unlikely or excluded (e.g. heart failure, influenza). However, the diagnosis remains a clinical one based on the opinion of the managing doctor

^Where a patient has been admitted to hospital for a non COVID-19 reason and develops COVID-19 symptoms whilst an in-patient, randomisation may occur up to 96 hours from onset of symptoms.

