## 7.2.1 Full Analysis Population

The primary analysis will be based on the intention-to-treat principle, which will include all participants who are randomised and received at least one dose of randomised therapy.

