## 7.6 Preliminary analysis

An analysis for preliminary efficacy and safety will be performed on an unlocked database using the full analysis population. The preliminary analysis will focus on the primary endpoints and a limited number of key secondary endpoints plus safety. The endpoints to be evaluated in the preliminary analysis are as follows:

Primary endpoint: Clinical Status on the WHO ordinal scale at day 29

Key secondary endpoints: Time to improvement on the ordinal scale, proportion of patients requiring mechanical ventilation, mortality, duration of hospitalization

Safety: Proportion of patients with one or more adverse events, proportion of patients with serious adverse events

Virologic efficacy of Brensocatib: Neutrophil elastase measurement in blood by treatment arm.

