#### 9.2.4 Time to discharge or to a NEWS of $\leq 2$

The endpoint will be analysed with a time-to-event framework. Cox models will be used, and the survivor function will be estimated. The hazard ratio and 95% confidence interval will be provided. Participants without the endpoint being analysed will be censored on the day of the last non-missing ordinal scale assessment. The

model will adjust for age and sites. Kaplan-Meier estimates for the time to event will also be plotted.

## 9.2.5 Change in NEWS from baseline to days 8, 15 and 29

Change in NEWS at specific time points will be summarized by proportions (e.g., proportion who have a 1-, 2-, 3-, or 4-point improvement or 1-, 2-, 3-, 4-point worsening). Mean changes from baseline to days 8, 15 and 29 will be reported.

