Hospitalised, on invasive mechanical ventilation or ECMO (Extracorporeal membrane oxygenation)

Death

Clinical status at Day 15 on the 7-point ordinal scale — no. of patients (%)

Not hospitalised, no limitations on activities

Not hospitalised, limitation on activities

Hospitalised, not requiring supplemental oxygen

Hospitalised, requiring supplemental oxygen

Hospitalised, on non-invasive ventilation or high flow oxygen devices

Hospitalised, on invasive mechanical ventilation or ECMO (Extracorporeal membrane oxygenation)

Death

Clinical status at Day 29 on the 7-point ordinal scale — no. of patients (%)

Not hospitalised, no limitations on activities

Not hospitalised, limitation on activities

Hospitalised, not requiring supplemental oxygen

Hospitalised, requiring supplemental oxygen

Hospitalised, on non-invasive ventilation or high flow oxygen devices

Hospitalised, on invasive mechanical ventilation or ECMO (Extracorporeal membrane oxygenation)

Death

Change in 7-point ordinal scale

Day 3

Day 5

Day 8

Day 11

Day 15

Day 29

Table 8: Secondary outcome: National Early Warning Score (NEWS)

	Brensocatib N =	Placebo N =	Effect estimate (95% CI)
Time to discharge or to a NEWS of <= 2			
Change in NEWS from baseline			
Day 8			
Day 15			
Day 29			

Table 9: Secondary outcome: Oxygenation, mechanical ventilation, hospitalisation, and mortality

Brensocatib	Placebo	Effect estimate (95% CI)
N =	N =	

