## Oxygenation

No of days free from oxygen

Duration of new oxygen use

Mechanical ventilation

Number of patients receiving new mechanical ventilation

No of days free from ventilation

Duration of new ventilation used

Duration of hospital stay - days

28-day mortality

Table 10: Safety analyses

	Brensocatib N =	Placebo N =	Effect estimate (95% CI)
% of patients with at least 1 AE			
Incidence of SAEs			
Discontinuation or temporary suspension of treatment			
Changes in white cell count			
Changes in haemoglobin			
Changes in platelets			
Changes in creatinine			
Changes in total bilirubin			
Changes in ALT			
Changes in AST			
Adverse events, n (%):			
Hyperkeratosis (Skin)			
Infections			
Dental complications			

Table 11: Adverse Events

Adverse Event - n (%)	Brensocatib	Placebo
	N =	N =
Death		
Life-threatening		
Required hospitalisation		
Resulted in persistent or significant disability		
Medically significant		
Total		

Table 12: Summary of all adverse events - System Organ Class Level

N = N =	Total	Placebo	Brensocatib
	N=	N =	N =

Number of participants

Number of participants with adverse events

Number of participants without adverse events

Number of adverse events

Cardiac disorders

Eye disorders

Gastrointestinal disorders

General disorders and administration site conditions

Infections and infestations

Injury, poisoning and procedural complications

Investigations

Metabolism and nutrition disorders

Musculoskeletal and connective

tissue disorders

Nervous system disorders

No Code

Psychiatric disorders

Renal and urinary disorders

Respiratory, thoracic and mediastinal disorders

Skin and subcutaneous tissue

disorders

Vascular disorders

Table 13: Summary of all adverse events - Preferred Term Level

Brensocatib	Placebo	Total
N =	N =	N=

Number of participants

Number of participants with adverse

events

Number of participants without adverse

events

Number of adverse events

Abdominal discomfort

Abdominal pain

Acute kidney injury

Arthralgia

Back pain

Blood glucose increased

Bradycardia

Cerebrovascular accident

Chest discomfort

Chest pain

Clostridium difficile infection

Constipation

Cough

Delirium

Diarrhoea

Dizziness

Drug eruption

Dry mouth

Dry skin

Dysarthria

Dyspepsia

Dyspnoea

Dysuria

Electrocardiogram abnormal

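### SAP 9.2.11 compares hospital stay between arms only in participants discharged alive by day 29, so the comparison is not between the randomised groups and would typically dilute a real benefit

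*SAP*

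**What the plan says.** SAP 9.2.11: "Duration of hospitalization will be calculated only for participants who are discharged alive on or prior to Day 29", with the arms compared by negative binomial regression. Deaths and participants still in hospital at day 29 drop out. No rule or sensitivity analysis brings them back for this endpoint.

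The protocol does not restrict the endpoint in this way. Protocol 3.7 lists duration of hospitalisation in days, with timepoint "Date of admission and discharge". Protocol 10.5 sets an all-treated population (randomised, at least one dose) for the primary analysis and any applicable secondary analyses. SAP 7.2.1 describes the matching full analysis population, which "will include all participants who are randomised and received at least one dose of randomised therapy". SAP 14 reports no changes to the protocol.

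On status, SAP 7.6 includes the endpoint among the key secondary endpoints of the preliminary analysis ("proportion of patients requiring mechanical ventilation, mortality, duration of hospitalization"). In SAP 16, the shell headed "Table 9: Secondary outcome: Oxygenation, mechanical ventilation, hospitalisation, and mortality" has a row "Duration of hospital stay - days" under a column for an effect estimate with 95% CI.

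**The concern.** Being alive and being discharged by day 29 are both determined after randomisation, and the trial hypothesises that brensocatib improves both clinical status and length of stay (protocol 1, SAP 3.1). If it does, more brensocatib than placebo participants enter the analysed set. The extra entrants are likely to be people who would otherwise have stayed longest or died. The estimate then mixes any effect on length of stay with the effect on who gets discharged.

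At stake is how one row of Table 9 is read. It would be printed with a confidence interval and look like a randomised comparison of stay. It is not one, and it would tend to understate a benefit.

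**Working it through.** **1. Inputs.** Placebo distribution: protocol 10.1, Table 4 (SAP 6, Table 2). Target odds ratio 1.75 and N = 400: protocol 10.1. Allocation 1:1: protocol 7.4. The documents give no distribution of length of stay, so steps 4 to 6 rest on assumptions.

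**2. Check of the planning figures.** Whitehead's formula is N = 12(z₀.₉₇₅ + z₀.₈₅)² / [(ln OR)²(1 − Σp̄³)], with (z₀.₉₇₅ + z₀.₈₅)² = 8.978.
- OR 2: 12 × 8.978 / (0.4805 × 0.8314) ≈ 270; the plan states 272.
- OR 1.75: about 410; the plan states 412.

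The distribution is therefore the one behind the plan's sample size.

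**3. Who is excluded.** The dead or hospitalised categories on placebo sum to 2 + 1 + 2 + 7 + 8 = 20%, odds 0.25.
- OR 1.75: 0.25/1.75 = 0.1429, share 0.1429/1.1429 = 12.5%. Excluded: 40 v 25 of 200. Analysed: 160 v 175.
- OR 2: 0.25/2 = 0.125, share 11.1%. Excluded: 40 v 22. The plan's own treatment column gives 1 + 0.5 + 1 + 3.8 + 4.7 = 11.0%.

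The day of this distribution is unclear: day 29 in the protocol text, day 28 in the SAP text, day 15 in the heading of protocol Table 6 and SAP Table 4. With an assumed placebo share at day 29 of 10% or 30%, the counts at OR 1.75 are 20 v 12 or 60 v 39. These categories also only approximate not being discharged alive by day 29, since readmission or death after discharge would differ.

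**4. Uniformly faster discharge (assumed exponential).** Let s be the share undischarged at day 29 and λ = −ln(s)/29. The mean with the undischarged and dead scored as 29 days is (1 − s)/λ. The mean in the discharged is [(1 − s)/λ − 29s]/(1 − s). At OR 1.75:

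| Placebo s | Brensocatib s | Discharged only (days) | Ratio | All, 29 if not discharged (days) | Ratio |
|---|---|---|---|---|---|
| 20% | 12.5% | 10.77 v 9.80 | 0.91 | 14.41 v 12.20 | 0.85 |
| 10% | 6.0% | 9.37 v 8.45 | 0.90 | 11.34 v 9.68 | 0.85 |
| 30% | 19.7% | 11.66 v 10.73 | 0.92 | 16.86 v 14.33 | 0.85 |

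In the first row the subset keeps ln 0.910 / ln 0.847 ≈ 56% of the log effect. The all-participant mean is a different estimand. It is used only as a yardstick for direction.

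**5. Other assumed shapes.** These are simulations with Weibull (shape 0.8 to 1.3) or log-normal (sigma 0.7 to 1.1) discharge times, matched to 20% v 12.5%. The subset ratio is 0.86 to 0.93, against 0.81 to 0.88 in everyone. With 200 per arm, power is 0.20 to 0.58 for the subset comparison (Wald test on the log ratio of means, standing in for the negative binomial). It is 0.63 to 0.80 for a log-rank test of time to live discharge with the undischarged and dead kept at risk to day 29.

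**6. Special case: late discharges only.** Suppose 160 placebo stays average 8 days, and brensocatib has the same 160 plus 15 extra discharges at day 22.
- Subset: (1280 + 330)/175 = 9.20 v 8.0, ratio 1.15.
- All: (1280 + 330 + 25 × 29)/200 = 11.68 v (1280 + 40 × 29)/200 = 12.20, ratio 0.96.
- Varying the mean stay over 6 to 12 days and the extra discharges over day 18 to 26: subset 1.04 to 1.29, all 0.92 to 0.99.

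**The case against.** **Other analyses show much of what is lost.** SAP 9.2.2 tabulates every category by arm at six days, so unequal exclusion would be visible. SAP 9.2.1 analyses time to a one-category improvement without this restriction, and for a participant at baseline category 3 that means leaving hospital. SAP 9.2.12 covers mortality. SAP 9.2.4 models time to discharge or NEWS of 2 or less. This stands as mitigation, but none of these corrects the Table 9 estimate. In particular, 9.2.4 counts a low NEWS in hospital as an event. Its rule that "Participants without the endpoint being analysed will be censored on the day of the last non-missing ordinal scale assessment" also does not say that deaths stay at risk to day 29.

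**A duration needs a discharge date.** The restriction may simply be how the SAP applied the protocol's admission and discharge dates. That explains a descriptive summary. It does not justify a between-arm test in the selected set.

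**The population conflict is limited.** SAP 7.2.1 is worded for the primary analysis, so on its own it does not contradict 9.2.11. Protocol 10.5 is the stronger text, and even there the word applicable leaves some room.

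**A reader might infer that the analysis would make an effective drug look harmful.** The documents do not support that as the expected result. It needs the benefit to fall mainly on late discharges. In step 6, shortening the other 160 stays from 8.0 to (1400 − 330)/160 = 6.69 days already brings the subset ratio back to 1. Protocol 2 says the effect builds over several days, but also hypothesises faster action in COVID-19, and the stated hypothesis is shorter stay.

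**A reader might also infer a raised false-positive rate.** If treatment affects no outcome, the selection is the same in both arms and causes no bias.

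**Conclusion.** The concern holds as a fault in the estimand and power of a secondary endpoint. As written, the comparison is not between the randomised groups, and exclusion is unequal under the trial's own planning effect: about 40 v 25 of 200, or 20 v 12 if the placebo share at day 29 is 10%. The usual consequence is dilution, 0.91 against 0.85 under the exponential assumption. Reversal is a special case. The counts rest on the planning distribution applying at day 29. The ratios and power figures rest on assumed discharge times and are illustrations, not bounds.

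The label of key secondary endpoint might suggest a confirmatory claim. SAP 7.6 uses it only for the preliminary analysis on an unlocked database, and SAP 7.8 sets no testing hierarchy. The primary endpoint is unaffected. The point should be fixed, but it does not threaten the trial's main conclusion.

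**What to change.** In SAP 9.2.11 and the stay row of shell Table 9, make the between-arm comparison time to live discharge through day 29 in the full analysis population:
- deaths before discharge kept as never discharged (at risk to day 29, or a Fine-Gray model);
- participants still in hospital censored at day 29;
- participants lost before discharge censored at their last known hospital status;
- adjustment for age and site, as in 9.2.4.

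Report days in hospital among those discharged alive by arm as a description, without a between-arm test.

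State the time origin. The protocol's measure runs from admission, and eligibility allows "Admitted to hospital as in-patient less than 96 hours prior to randomisation", or longer where COVID-19 began in hospital. Moving the origin to day 1 is optional and is not needed to cure the selection. If it is done, record it in SAP 14.

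Cost: SAP wording, one re-programmed analysis and one table row. Admission, discharge and death dates are already collected (protocol 3.7). The downside is that a discharge hazard ratio is less intuitive than a difference in mean days.

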#### 9.2.12 28-day mortality

All-cause mortality will be estimated using the Kaplan-Meier product limit method with all available data. The treatment arms will be compared using the log-rank test, and hazard ratios and 95% confidence intervals will be provided. Participants who did not die will be censored on the last study day.

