7.4. The randomisation scheme

Participants will be allocated to receive either Brensocatib (25mg once daily for 28 days) or placebo in addition to standard of care. Randomisation will be 1:1 intervention:placebo. Randomisation will be stratified by site and age: <65 years/≥65 years.

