10.2. Statistical analysis plan

The primary analysis will be based on an intention-to-treat population, including participants randomized. Similarly, safety analyses will be based a modified intent-to-treat population consisting of all participants who were randomized.

This is a controlled randomized trial testing a superiority hypothesis with a two-sided type I error rate of 0.05. Secondary hypotheses have been ordered according to relative importance. These will be described according to the appropriate summary statistics (e.g., proportions for categorical data, means with 95% confidence intervals for continuous data, median for time-to-event data).

A statistical analysis plan (SAP) will be prepared for analysis of primary and secondary outcomes and will include a plan for handling missing data.

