## 5.3 Randomisation and Blinding

Participants will be allocated to receive either Brensocatib (25mg once daily for 28 days) or placebo in addition to standard of care. Randomisation will be 1:1 intervention:placebo. Randomisation will be stratified by site and age: <65 years/≥65 years. Randomisation will be done centrally using a web-based validated randomisation program provided by Tayside Clinical Trials Unit. The trial is doubled-blind, participants and trial staff are blind to allocation, unblinding will take place after database lockdown. Emergency unblinding procedures are described in section 7.6 of the protocol.

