Prior to the commencement of the trial, we took the anticipated WHO scenario and the odds ratio of 2 which required enrolment of 272 participants. Allowing for a potential loss to follow–up of 9% (27 participants) this meant we will required 300 participants (150 per arm) to achieve 85% power at 5% significance. This was subsequently reviewed as part of a pre–specified blinded sample size re–evaluation by an independent statistician. The results of this re–evaluation, using data for the primary endpoint available in December 2020 found that 300 patients enrolled would provide approximately 88% power to detect an odds ratio of 2.0. This, along with the results of other COVID–19 trials were reviewed by the Trial Steering Committee (TSC) and DMC who noted that other COVID–19 therapeutics had achieved odds ratios lower than 2.0 in the majority of cases. Based on this, the TSC and DMC recommended targeting an odds ratio of 1.75. At least 80% power for an odds ratio of 1.75 requires enrolment of a minimum of 360 patients with 400 patients provided approximately 85% power. A final sample size of 400 subjects was therefore recommended by the TSC and subsequently approved by the DMC in December 2020 (Appendix 1).

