## 7.7 Multi-centre Studies

(ICH E3;9.7.1, 11.4.2.4. ICH E9; 3.2)

This is a multi-centre trial recruiting from 15 NHS Trusts/Boards within UK, if required to fulfil recruitment more NHS Trusts/Boards will be added.

Centre will be treated as random effect in the mixed ordinal logistic regression model and analysis of secondary outcomes.

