## 9.2.8 Number of patients receiving new mechanical ventilation

The number and percentage of participants who received new mechanical ventilation will be presented. Comparison between the treatment arms will be performed using a Fisher's Exact test.

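### The mortality and new-ventilation comparisons in the SAP make no use of the randomisation strata, leave the effect measure or its model unstated, and conflict with SAP 7.7

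*SAP*

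**What the plan says.** - **Randomisation.** Protocol 7.4: "Randomisation will be stratified by site and age: <65 years/≥65 years". Protocol 4 gives the reason for the age stratum: age predicts severe disease and death.
- **Mortality.** SAP 9.2.12: "The treatment arms will be compared using the log-rank test". Hazard ratios with 95% intervals are promised, but the section gives no strata, covariates or model for them.
- **New mechanical ventilation.** SAP 9.2.8 gives counts and percentages, then: "Comparison between the treatment arms will be performed using a Fisher's Exact test". It names no effect measure or interval.
- **Centre.** SAP 7.7: "Centre will be treated as random effect in the mixed ordinal logistic regression model and analysis of secondary outcomes".
- **Comparable analyses.** SAP 9.1 adjusts the primary model for age, with site as a random effect. The Cox models in SAP 9.2.1 and 9.2.4 adjust for age and site.
- **Reporting shell.** SAP Table 9 has a column for an effect estimate with its 95% interval, and both outcomes are rows of that table.
- **Use.** SAP 7.6 lists mortality and mechanical ventilation among the key secondary endpoints of the preliminary analysis on an unlocked database.

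**The concern.** When randomisation is stratified on a prognostic factor, the arms are balanced on it by design. A test that ignores the factor uses a variance that is too large for that design, so it tends to reject too rarely and loses some power. The SAP adjusts for age on the ordinal scale and on time to improvement, but not on death, the outcome the protocol cites as a reason to stratify by age.

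A plain log-rank test and a Fisher test also have no place for a centre effect, so 9.2.8 and 9.2.12 cannot be carried out as written while respecting 7.7. Two choices stay open to the analyst: which model gives the mortality hazard ratio, and what fills the estimate column for ventilation. Both should be settled before unblinded results are seen.

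**Working it through.** **1. The plan's own figures.** These concern the primary endpoint only. The test is described as "testing a superiority hypothesis with a two-sided type I error rate of 0.05" (Protocol 10.2), allocation as "Randomisation will be 1:1 intervention:placebo" (SAP 5.3), and "the TSC and DMC recommended targeting an odds ratio of 1.75" (SAP 6). The formula for ordered categories is N = 12(z₀.₉₇₅ + z_power)² / [(ln OR)²(1 − Σp̄ᵢ³)], with the control distribution from SAP Table 2.
- OR 1.75, 85% power: 12(1.960 + 1.036)² / [0.3132 × (1 − 0.160)] = 410 (stated 412).
- OR 2.0, 85% power: 12(1.960 + 1.036)² / [0.4805 × (1 − 0.169)] = 270 (stated 272).
- Power at OR 1.75: 80.2% with 360 patients and 84.2% with 400, against the SAP's "a minimum of 360 patients with 400 patients provided approximately 85% power".

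The stated figures reproduce. No power is stated for death or ventilation.

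**2. Mortality at the planning rate.** Control risk is 2% (SAP Table 2). At OR 1.75 the treated risk is 0.02 / (0.02 + 1.75 × 0.98) = 1.15%.
- Expected deaths: 200 × (0.02 + 0.0115) = 6.3.
- Hazard ratio: ln(1 − 0.0115) / ln(1 − 0.02) = 0.573.
- Power (Schoenfeld): Φ(½√6.3 × |ln 0.573| − 1.96) = Φ(−1.26) = about 10%.
- Deaths needed for 80% power at HR 0.57: 4(1.960 + 0.842)² / (ln 0.57)² = 100.

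**3. Cost of ignoring age, and of Fisher's test.** Simulation: 400 patients, 1:1 within age groups, treatment HR 0.57, 20,000 runs per row. Only the 2% risk comes from the documents. The other risks, the age hazard ratios and the age mix are assumptions. Site was not simulated. Entries are power in %; LR is log-rank and CMH is the age-stratified Cochran-Mantel-Haenszel test.

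| Control risk | Age HR | Share ≥65 | LR plain | LR by age | Fisher | Pearson | CMH by age |
|---|---|---|---|---|---|---|---|
| 2% | 6 | 50% | 9.1 | 9.1 | 3.5 | 9.1 | 9.1 |
| 10% | 3 | 50% | 32.8 | 33.6 | 26.6 | 32.3 | 33.9 |
| 10% | 6 | 35% | 31.6 | 34.0 | 25.0 | 30.9 | 33.8 |
| 10% | 10 | 35% | 30.9 | 34.5 | 24.5 | 30.3 | 34.3 |
| 20% | 3 | 50% | 58.2 | 60.0 | 52.6 | 58.4 | 59.7 |
| 20% | 6 | 35% | 55.0 | 60.7 | 49.1 | 55.2 | 59.9 |

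Differences, in points, in row order:
- Log-rank, age ignored: 0, 0.8, 2.4, 3.6, 1.8, 5.7.
- Binary outcome, age ignored (CMH minus Pearson): 0, 1.6, 2.9, 4.0, 1.3, 4.7.
- Fisher's conservatism alone (Pearson minus Fisher): 5.6, 5.7, 5.9, 5.8, 5.8, 6.1.

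The Pearson column separates the two causes. In every row the exact test costs more than the missing age term.

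**4. Size under the null.** Fisher's true size at nominal 5%, by enumeration of two binomials with 200 per arm, is 1.7%, 2.2%, 2.9% and 3.4% at event rates of 2%, 3%, 5% and 10%. Unadjusted Pearson gives 4.5 to 4.8% at the same rates. With 20% risk and age HR 6 (4,000 runs), the plain log-rank rejects 3.6% of the time and the age-stratified log-rank about 5%.

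**The case against.** The strongest reply is that nothing here is invalid. Both tests hold their size. SAP 7.3.1 promises adjustment for site and age only for the primary analysis, so unadjusted secondary tests do not breach that rule. Neither endpoint is powered, SAP 7.8 sets no testing order, and Protocol 10.2 treats secondary hypotheses descriptively. At the only death rate in the documents, stratifying gains nothing, because about six deaths limit power whatever the test. The missing strata in 9.2.12 are inferred from silence. The negative binomial analyses in SAP 9.2.6, 9.2.7 and 9.2.9 to 9.2.11 also name no age or centre term.

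All of this stands, and it limits the size of the point. It does not remove the conflict with 7.7, the unspecified hazard-ratio model, or the empty estimate column for ventilation. The 2% figure is also not a firm ceiling, since the SAP itself calls its assumptions very uncertain. The 1% ventilation figure in SAP Table 2 is status on one day, so it does not bound cumulative new ventilation.

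A reader might infer that omitting the strata inflates false positives. The size figures show the opposite. A reader might also blame the whole gap between Fisher and an age-stratified test, about 6 to 11 points, on the missing age term. Only 0 to about 5 points of it come from age.

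**Conclusion.** The inconsistency holds on the text: two key secondary outcomes are analysed without the randomisation strata, against SAP 7.7 and unlike the SAP's own Cox analyses, and their effect estimates are under-specified. For Fisher's test the lack of adjustment follows from the method; for the log-rank it follows from nothing being named.

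The statistical cost is modest. At a treatment hazard ratio of 0.57, ignoring age costs about 1 to 6 points of power at assumed risks of 10 to 20%, the upper end needing a strong age effect, and nothing at the planned 2%. Fisher's conservatism costs a further 5 to 7 points on the ventilation comparison. These ranges are illustrative, because the age effect, the age mix and the higher risks are not in the documents. The cost of ignoring site was not estimated. The primary analysis and the stated sample size and power are unaffected. The change is worth making because it is free and closes open choices.

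**What to change.** - **SAP 9.2.12.** Specify a log-rank test stratified by age group, with the hazard ratio and 95% interval from a Cox model adjusted for age group and with site as a shared frailty, as 7.7 implies. Site is better as a random effect than as a stratum: 15 sites × 2 age groups = 30 cells, or about 13 patients each (400 / 30).
- **SAP 9.2.8.** Specify a logistic model adjusted for age group with site as a random effect, or an age-stratified Mantel-Haenszel test and estimate. Report an odds ratio or risk difference with its 95% interval, so that Table 9 can be filled. If the Mantel-Haenszel route is chosen, state in 7.7 that centre is not modelled for this outcome.
- **Sparse data.** Keep Fisher's test only under a written rule, such as a stated minimum total event count or failure of the model to converge, fixed before unblinding. State likewise what is reported for mortality if the frailty model cannot be fitted; with about six deaths this may well be needed.
- **SAP 7.3.1.** Say which secondary analyses adjust for age and site, including the negative binomial models.

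The cost is SAP wording and minor programming. No new data are needed.
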